**12.10.8. Pharmacokinetic Tables**

Pharmacokinetic: Tables					
No.	Population	IDSL / Example Shell	Title	Programming Notes	Deliverable [Priority]
Secondary: Pharmacokinetic					
4.1.	PK		Summary of PK Serum Concentrations of GSK3772847		SAC only
4.2.	PK		Summary of Incidence and Titres of Anti-GSK3772847 Antibodies		SAC only

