Objectives	Endpoints
	
Week 16.
 
 
• Change from baseline in SGRQ total score at Weeks 4, 8, 12 and 16.
 
• Proportion of St. George's Respiratory Questionnaire (SGRQ) responders (at least a 4 unit improvement from baseline) at Weeks 4, 8, 12 and 16.
 
• Change from baseline in pre-bronchodilator FEV1 at Weeks 2, 4, 6, 8, 10, 12, 14, 16.
 
• Change from baseline in mean morning peak expiratory flow (PEF) and mean evening PEF over each four weeks of the 16 week treatment period.
 
• Change from baseline in mean daytime asthma symptom score over each four weeks of the 16 week treatment period.
 
• Change from baseline in rescue medication use (albuterol/salbutamol): mean number of inhalations per day over each four weeks of the 16 week treatment period.
 
• Changes from baseline in night-time awakenings due to asthma symptoms requiring rescue medication use over each four weeks of the 16 week treatment period.
 
• Change from baseline in fractional exhaled nitric oxide (FeNO) at each week measured.
 

 
• To evaluate the safety and tolerability of GSK3772847, compared with placebo administered intravenously every 4 weeks for 12 weeks (Week 0-12, 4 doses in total) in participants with moderately severe asthma.
 
	
 
• Incidence and frequency of adverse events (AEs) and serious adverse events (SAEs).
 
• Change from baseline in vital signs at weeks 1, 2, 4, 6, 8, 10, 12, 14, 16, 20, 24 and 28.
 
• Change between post-dose and pre-dose in vital signs at weeks 0, 4, 8 and 12.
 
• Change from baseline in 12-lead electrocardiogram (ECG) measurements at weeks 4, 8, 12 and 16.
 
• Change between post-dose and pre-dose in 12-lead ECG measurements at weeks 0, 4, 8 and 12.
 
• Change from baseline in 24 hours Holter measurements at weeks 4 and 12.
 
• Change from baseline in clinical chemistry at weeks 2, 4, 8, 12, 16 and 28.
 
• Change from baseline in haematology and cardiac markers at weeks 1, 2, 4, 6, 8, 10, 12, 14, 16 and 28.
 
• Incidence of and titres of anti- GSK3772847 antibodies at weeks 2, 4, 8, 12, 16, 20, 24 and 28.
 

Objectives	Endpoints

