Modified Intent-to-Treat excluding GCP non-compliant subjects	
 
The Modified Intent-to-Treat excluding GCP non-compliant subjects (mITT) population will consist of all randomised participants who take at least 1 dose of study treatment, excluding participants where an investigation by GSK has shown that good clinical practice has not been followed. Any participants excluded from this population will be identified as protocol deviations and listed in a separate output. Participants will be analysed according to the treatment they receive
 
	
 
Efficacy (all except loss of control)
 

Population	Definition / Criteria	Analyses Evaluated
	>=50% of the time. If the participant receives 50% of each treatment they will be analysed according to the randomised treatment.	
Safety including GCP non-compliant subjects	
 
The Safety (SAFF_ALL) population will consist of all randomised participants who take at least 1 dose of study treatment. Participant will be analysed according to the treatment they receive >=50% of the time. If the participant receives 50% of each treatment they will be analysed according to the randomised treatment.
 
	
 
Study population
 
Inclusion, exclusion and randomisation criteria deviations
 
Participant disposition
 
Safety
 

Pharmacokinetic	
 
The PK population will consist of all randomised participants who received at least one dose of study medication, and for whom at least one pharmacokinetic sample was obtained, analysed and was measurable.
 
	
 
PK
 

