## **8. SAFETY ANALYSES**

The safety analyses will be based on the Safety including GCP non-compliant subjects population, unless otherwise specified. The details of the planned displays are provided in [Appendix 10: List of Data Displays](#).

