### **9.1. Secondary Pharmacokinetic Analyses**

#### **9.1.1. Endpoint / Variables**

Serum concentrations of GSK3772847 by nominal time.

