**CONFIDENTIAL**

207597

Non-ICH: Listings					
No.	Population	IDSL / Example Shell	Title	Programming Notes	Deliverable [Priority]
51.	mITT		List of Free and Total Soluble ST2 Concentrations		
Adverse Events					
52.	SAFF_ALL		Listing of Clinical Chemistry		ETP, SAC
53.	SAFF_ALL		Listing of Haematology and Cardiac Markers		ETP, SAC
54.	SAFF_ALL		Listing of Anti-GSK3772847 Antibodies		ETP, SAC
55.	SAFF_ALL	ESI8	Listing of AE Terms of Special Interest	IDSL	ETP, SAC
Exploratory Biomarker					
56.	mITT		Listing of Induced Sputum and Exploratory Serum Biomarkers		ETP, SAC
Medical History					
57.	SAFF_ALL	MH2	Listing of Medical Conditions at Screening		ETP, SAC
58.	SAFF_ALL	SP5	Listing of Family History of Cardiovascular Disorders		ETP, SAC
59.	SAFF_ALL	SP6	Listing of Asthma History		ETP, SAC
60.	SAFF_ALL	SP7	Listing of Smoking History and Smoking Status		ETP, SAC
61.	SAFF_ALL	CM6	Relationship between ATC Level 1, Ingredient and Verbatim Text		ETP, SAC
Liver Events: Note only produced if there is a Liver Event					
62.	SAFF_ALL	LIVER5	Listing of Liver Events		ETP, SAC
63.	SAFF_ALL	LIVER6	Listing of Liver Event Information for RUCAM Score		ETP, SAC
64.	SAFF_ALL	LIVER7	Listing of Liver Biopsy		ETP, SAC

Non-ICH: Listings					
No.	Population	IDSL / Example Shell	Title	Programming Notes	Deliverable [Priority]
65.	SAFF_ALL	LIVER8	Listing of Liver Imaging Details		ETP, SAC
Cardiovascular Events: Note only produced if there is a Cardiovascular Event					
66.	SAFF_ALL	Patient Profile	Listing of Myocardial infarction/unstable angina		ETP, SAC
67.	SAFF_ALL	Patient Profile	Listing of Congestive heart failure		ETP, SAC
68.	SAFF_ALL	Patient Profile	Listing of Arrhythmias		ETP, SAC
69.	SAFF_ALL	Patient Profile	Listing of Valvulopathy		ETP, SAC
70.	SAFF_ALL	Patient Profile	Listing of Pulmonary hypertension		ETP, SAC
71.	SAFF_ALL	Patient Profile	Listing of Cerebrovascular events/stroke and transient ischemic attack		
72.	SAFF_ALL	Patient Profile	Listing of Peripheral arterial thromboembolism		
73.	SAFF_ALL	Patient Profile	Listing of Deep venous thrombosis/pulmonary embolism		
74.	SAFF_ALL	Patient Profile	Listing of Revascularisation		
75.	SAFF_ALL	Patient Profile	Listing of Deaths		

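### The only summary table of anti-drug antibodies (Table 4.2) is set on the PK population, which on its plain reading leaves out essentially the whole placebo arm

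*SAP*

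**What the plan says.** Section 2.3 gives the safety objective as "To evaluate the safety and tolerability of GSK3772847, compared with placebo administered intravenously every 4 weeks for 12 weeks". Among the endpoints under that objective is "Incidence of and titres of anti- GSK3772847 antibodies at weeks 2, 4, 8, 12, 16, 20, 24 and 28". The endpoint is not listed under the PK objective.

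Section 8.5, inside the Safety Analyses section, plans summaries of antibody incidence and titres from Week 0 (pre-dose) to Week 28 and names no population of its own. The rule for the whole of Section 8 is: "The safety analyses will be based on the Safety including GCP non-compliant subjects population, unless otherwise specified".

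The notes to Section 4 make Appendix 10 the place where each display's population is fixed. There, Section 12.10.8 lists Table 4.2, "Summary of Incidence and Titres of Anti-GSK3772847 Antibodies", on the PK population. Section 4 defines that population as randomised, dosed participants "for whom at least one pharmacokinetic sample was obtained, analysed and was measurable". Section 9.1.1 gives the PK variable as "Serum concentrations of GSK3772847 by nominal time".

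Listing 54 in Section 12.10.13, "Listing of Anti-GSK3772847 Antibodies", is on SAFF_ALL.

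**The concern.** Antibody incidence is a safety endpoint under an objective that compares active drug with placebo. Its only summary table is restricted to participants in whom drug could be measured. Placebo participants receive no drug, so the restriction removes the comparator from the table.

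The placebo arm shows how often the assay turns positive over 28 weeks of sampling in people not exposed to the drug, whether through new reactivity or false positives. The active arm alone cannot show this. Followed as written, the plan would report antibody incidence on GSK3772847 with no summarised reference rate beside it, although placebo results are expected, since Listing 54 covers both arms.

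**Working it through.** The plan gives no figure on this point to reproduce. The check sets the rules side by side, then sizes the result.

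**Which population applies to Table 4.2**

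1. Section 8 sets SAFF_ALL as the default for safety analyses and allows exceptions.
2. Section 8.5 covers antibodies and specifies no exception.
3. Section 4 (notes) sends the reader to Appendix 10 for the population of each display.
4. Appendix 10, Section 12.10.8, puts Table 4.2 on PK, so the table would be programmed on PK.
5. The safety tables in Section 12.10.7 (3.1 to 3.43) include no antibody table, so Table 4.2 is the only summary.
6. Listing 54 puts the same data on SAFF_ALL.

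This is current text. The superseded plan bound in the same file lists only Table 4.1 among its PK tables.

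**What separates the two populations**

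SAFF_ALL and the PK population both start from all randomised participants with at least one dose, and neither excludes participants for GCP non-compliance. The only further membership condition for PK is a sample that was obtained, assayed and measurable. That condition does all the excluding. Because the analyte is GSK3772847, it excludes placebo participants, apart from any who received active drug in error.

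**Size**

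Inputs: 70 evaluable participants per arm (Section 2.6) and 1:1 allocation (Section 2.4). The 70 belongs to the primary endpoint's sample size, so it only stands in for the number dosed.

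| Population for Table 4.2 | GSK3772847 | Placebo | Total |
|---|---|---|---|
| PK, as written | about 70 | about 0 | about 70 |
| SAFF_ALL | about 70 | about 70 | about 140 |

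About 70 of 140, or half of the dosed participants, would be absent from the table.

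**What the placebo arm would add**

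Take the case of no positives among 70 placebo participants, chosen only to show the available precision. The upper exact bound on the background rate is 1 − α^(1/n):

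- one-sided 95%: 1 − 0.05^(1/70) = 0.042, or 4.2%
- two-sided 95%: 1 − 0.025^(1/70) = 0.051, or 5.1%

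On the PK population the placebo denominator is about 0, and Table 4.2 supports no such bound.

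**The case against.** **The choice is formally allowed.** The Section 8 default permits exceptions, and Appendix 10 is where they are made. That stands, but the SAP gives no reason for this exception, and it works against the endpoint's own objective and against Listing 54.

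**Placebo data are not lost.** This stands. Listing 54 reports them at both the end-of-treatment and final deliveries, and a reader could count positives by hand. A listing is still not a summary of incidence by arm.

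**Pre-existing positivity is already visible.** A reader might infer that, without placebo, background positivity cannot be separated from drug-induced antibodies. The SAP does not support that: Section 8.5 and the sampling schedule in Appendix 2 include a Week 0 pre-dose immunogenicity sample, so pre-existing reactivity can be seen within the active arm. What the pre-dose sample cannot give is the rate of new or false-positive results over later visits without drug.

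**No formal comparison is planned.** The comparison with placebo is the wording of the overall safety objective, and Section 8.5 plans descriptive summaries without a test. That stands, but even a descriptive comparison needs both arms in the table.

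**Exclusion of placebo is an inference.** The SAP does not define measurable or say whether placebo PK samples are assayed, and the schedule does not limit PK sampling to the active arm. Placebo could stay in only if those samples were assayed and results below quantification counted as measurable, which is not the plain reading.

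**Treated participants with no measurable drug.** A reader might infer that the active denominator is also materially distorted. Nothing supports that: PK is sampled after the Week 0 infusion and repeatedly afterwards, so such losses are probably trivial.

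**Conclusion.** The point holds as a wrong population assignment for one safety table. As written, the only antibody summary covers about 70 active participants and essentially none of about 70 on placebo. It contradicts the safety objective in Section 2.3, the population that Section 8.5 inherits, and Listing 54.

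The consequence is narrow: no table gives antibody incidence by arm, so new or false-positive results without drug are not summarised for comparison. The primary analysis is unaffected.

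A reader might go further and claim that a particular incidence on active drug would be uninterpretable. The SAP gives no background antibody rate, so any such example would be hypothetical.

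The conclusion rests on two assumptions: that measurable means a quantifiable drug concentration, and that 70 per arm approximates the number dosed. The second affects only the size. The first decides whether placebo is excluded, but the mismatch between Table 4.2 and Listing 54 remains either way.

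**What to change.** In Appendix 10, Section 12.10.8, change the population of Table 4.2 from PK to SAFF_ALL and present the table by treatment arm, in line with Section 8.5 and Listing 54. If a summary of the active arm alone is intended, the SAP should say so and give the reason.

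The cost is one cell in Appendix 10. No new sampling or data are needed, because Listing 54 already uses the antibody results on SAFF_ALL. Showing baseline and post-baseline positivity separately would help interpretation, but it is a matter for the table shell. The shells are not in the file, so its absence cannot be claimed.

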## 12.10.9. Pharmacodynamic and Biomarker Tables

Pharmacodynamic and Biomarker: Tables					
No.	Population	IDSL / Example Shell	Title	Programming Notes	Deliverable [Priority]
Secondary: Pharmacodynamic					
6.1.	mITT		Summary of Raw and Percentage Change from Baseline in Free Soluble ST2 concentration (ug/L) (On-treatment)	Pre and Post dose.	ETP, SAC
6.2.	mITT		Analysis of Percentage Change from Baseline in Free Soluble ST2 concentration (ug/mL) (On-treatment)	Pre dose only.	ETP, SAC
6.3.	mITT		Summary of Raw and Percentage Change from Baseline in Free soluble ST2 concentration (ug/L) (Post-treatment)		ETP, SAC
6.4.	mITT		Analysis of Percentage Change from Baseline in Free soluble ST2 concentration (ug/mL) (Post-treatment)		ETP, SAC
6.5.	mITT		Summary of Raw and Percentage Change from Baseline in Total Soluble ST2 concentration (ug/L) (On-treatment)	Pre and Post dose.	ETP, SAC
6.6.	mITT		Analysis of Percentage Change from Baseline in Total Soluble ST2 concentration (ug/L) (On-treatment)	Pre dose only.	ETP, SAC
6.7.	mITT		Summary of Raw and Percentage Change from Baseline in Total Soluble ST2 concentration (ug/L) (Post-treatment)		ETP, SAC
6.8.	mITT		Analysis of Percentage Change from Baseline in Total Soluble ST2 concentration (ug/L) (Post-treatment)		ETP, SAC
Exploratory: Biomarkers					
6.9.	mITT		Summary and Change from Baseline in Induced Sputum Biomarkers (subset) at Weeks 8 and 16	Include geometric mean and %CV	ETP, SAC
6.10.	mITT		Summary and Change from Baseline in Exploratory Serum Markers at Weeks 8 and 16	Include geometric mean and %CV	ETP, SAC

12.10.10. Pharmacokinetic Figures

Pharmacokinetic: Figures					
No.	Population	IDSL / Example Shell	Title	Programming Notes	Deliverable [Priority]
Secondary: Pharmacokinetic					
6.1.	PK		Plot of Serum Concentrations of GSK3772847 over Time		ETP, SAC
6.2.	PK		Pre-dose Trough Concentration of GSK3772847 vs Eosinophils at Week 4		ETP, SAC
6.3.	PK		Pre-dose Trough Concentration of GSK3772847 vs FeNO at Week 4		ETP, SAC
6.4.	PK		Pre-dose Trough Concentration of GSK3772847 vs IgE at Week 4		ETP, SAC

## 12.10.11. Pharmacodynamic and Biomarker Figures

Pharmacodynamic: Figures					
No.	Population	IDSL / Example Shell	Title	Programming Notes	Deliverable [Priority]
Secondary: Pharmacodynamic					
6.5.	mITT		Plot of Percentage Change from Baseline in Free Soluble ST2 levels (On-treatment)		ETP, SAC
6.6.	mITT		Plot of Percentage Change from Baseline in Free soluble ST2 levels (Post-treatment)		ETP, SAC
6.7.	mITT		Plot of Percentage Change from Baseline in Total Soluble ST2 levels (On-treatment)		ETP, SAC
6.8.	mITT		Plot of Percentage Change from Baseline in Total Soluble ST2 levels (Post-treatment)		ETP, SAC
6.9.	mITT_LoC		Loss of Control Over Weeks 0-16 vs Free soluble ST2 by Treatment – Fractional Polynomial Model (Primary Estimand)		ETP, SAC
6.10.	mITT_LoC		Loss of Control Over Weeks 0-16 vs Free soluble ST2 Treatment Difference – Fractional Polynomial (Primary Estimand)		ETP, SAC
6.11.	mITT_LoC		Loss of Control Over Weeks 0-16 vs Free soluble ST2 by Treatment – Fractional Polynomial Model (Secondary Estimand)		ETP, SAC
6.12.	mITT_LoC		Loss of Control Over Weeks 0-16 vs Free soluble ST2 Treatment Difference – Fractional Polynomial (Secondary Estimand)		ETP, SAC

## 12.10.12. ICH Listings

ICH: Listings					
No.	Population	IDSL / Example Shell	Title	Programming Notes	Deliverable [Priority]
Subject Disposition					
1.	Screened	ES7	Listing of Reasons for Screen and Run-in Failure	Journal Guidelines	ETP, SAC
2.	SAFF_ALL	ES2 / ES3	Listing of Reasons for Study Withdrawal	ICH E3	ETP, SAC
3.	SAFF_ALL	SD2/SD3	Listing of Reasons for Study Treatment Discontinuation	ICH E3	ETP, SAC
4.	SAFF_ALL	BL1 / BL2	Listing of Participants for Whom the Treatment Blind was Broken	ICH E3	ETP, SAC
5.	SAFF_ALL	TA1 / CP_RD1x	Listing of Planned and Actual Treatments	IDSL	ETP, SAC
Protocol Deviations					
6.	SAFF_ALL	DV2	Listing of Important Protocol Deviations	ICH E3	ETP, SAC
7.	SAFF_ALL	IE3	Listing of Subjects with Inclusion/Exclusion Criteria Deviations	ICH E3	ETP, SAC
Populations Analysed					
8.	SAFF_ALL		Listing of Participants Excluded from Any Population (GCP non compliance)	ICH E3.	ETP, SAC
Demographic and Baseline Characteristics					
9.	SAFF_ALL	DM2	Listing of Demographic Characteristics	ICH E3	ETP, SAC
10.	SAFF_ALL	DM9	Listing of Race	ICH E3	ETP, SAC

**CONFIDENTIAL**

207597

ICH: Listings					
No.	Population	IDSL / Example Shell	Title	Programming Notes	Deliverable [Priority]
Prior and Concomitant Medications					
11.	SAFF_ALL	CP_CM3	Listing of Concomitant Medications	IDSL	ETP, SAC
Exposure and Treatment Compliance					
12.	SAFF_ALL	EX3	Listing of Exposure Data	ICH E3	ETP, SAC
Adverse Events					
13.	SAFF_ALL	AE8	Listing of All Adverse Events	ICH E3	ETP, SAC
14.	SAFF_ALL	AE7	Listing of Subject Numbers for Individual Adverse Events	ICH E3	ETP, SAC
15.	SAFF_ALL	AE8	Listing of Adverse Events Leading to Withdrawal from Study / Permanent Discontinuation of Study Treatment	ICH E3	ETP, SAC
16.	SAFF_ALL	AE2	Listing of Relationship Between Adverse Event System Organ Classes, Preferred Terms, and Verbatim Text	IDSL	ETP, SAC
Serious and Other Significant Adverse Events					
17.	SAFF_ALL	AE8	Listing of Fatal Serious Adverse Events	ICH E3	ETP, SAC
18.	SAFF_ALL	AE8	Listing of Non-Fatal Serious Adverse Events	ICH E3	ETP, SAC
19.	SAFF_ALL	AE14	Listing of Reasons for Considering as a Serious Adverse Event	ICH E3	ETP, SAC
20.	SAFF_ALL	AE8	Listing of Serious Adverse Events Leading to Withdrawal from Study / Permanent Discontinuation of Study Treatment	ICH E3	ETP, SAC
21.	SAFF_ALL	AE8	Listing of Adverse Events of Special Interest	ICH E3	ETP, SAC

ICH: Listings					
No.	Population	IDSL / Example Shell	Title	Programming Notes	Deliverable [Priority]
Hepatobiliary (Liver)					
22.	SAFF_ALL	MH2	Listing of Medical Conditions for Participants with Liver Stopping Events	IDSL	ETP, SAC
23.	SAFF_ALL	SU2	Listing of Substance Use for Participants with Liver Stopping Events	IDSL	ETP, SAC
All Laboratory					
24.	SAFF_ALL	LB5 / LB6	Listing of All Laboratory Data for Participants with Any Value Outside Normal Range	ICH E3	ETP, SAC
25.	SAFF_ALL	LB14	Listing of Laboratory Data with Character Results	ICH E3	ETP, SAC
ECG					
26.	SAFF_ALL	EG5	Listing of All ECG Findings for Participants with an Abnormal ECG Finding	IDSL	ETP, SAC
27.	SAFF_ALL	EG5	Listing of Abnormal ECG Findings	IDSL	ETP, SAC
Holter					
28.	SAFF_ALL	MH6	Listing of Holter R-on-T Beat Data	IDSL	ETP, SAC
29.	SAFF_ALL	MH7	Listing of Holter {Supraventricular} {Ventricular} Event Data	IDSL, Update title as appropriate based on data	ETP, SAC
30.	SAFF_ALL	MH8	Listing of Holter {Sustained} {Non-sustained} {Supraventricular} {Ventricular} Run	IDSL, Update title as appropriate based on data	ETP, SAC
31.	SAFF_ALL	MH9	Listing of Holter Atrial {Fibrillation} {Flutter} Data	IDSL, Update title as appropriate based on data	ETP, SAC
32.	SAFF_ALL	MH10	Listing of Holter Abnormalities	IDSL	ETP, SAC

ICH: Listings					
No.	Population	IDSL / Example Shell	Title	Programming Notes	Deliverable [Priority]
Vital Signs					
33.	SAFF_ALL	VS4	Listing of All Vital Signs Data	IDSL	ETP, SAC
Primary Analysis Data: Loss of Asthma Control and Intercurrent Events					
34.	mITT_LoC		Listing of Loss of Asthma Control	Include all reasons for loss of control and time to loss of asthma control	ETP, SAC
35.	mITT_LoC		Listing of Intercurrent Events	Include treatment subject was analysed as taking and treatment at time of loss of control	ETP, SAC

## 12.10.13. Non-ICH Listings

Non-ICH: Listings					
No.	Population	IDSL / Example Shell	Title	Programming Notes	Deliverable [Priority]
Study Population					
36.	SAFF_ALL	SP2	Listing of the Follow-up Contact		ETP, SAC
37.	SAFF_ALL	TA1	Listing of Treatment Misallocations	Change Centre ID to Investigator ID: xxxxxx and also Investigator at Centre: xxxxxx	ETP, SAC
38.	SAFF_ALL	SP4	Listing of Overall Percentage Treatment Compliance		ETP, SAC
Secondary Efficacy					
39.	mITT		Listing of Eosinophils	Include randomisation and analysis strata	ETP, SAC
40.	mITT	SP10	Listing of Lung Function Results at Screening		ETP, SAC
41.	mITT	SP10	Listing of Lung Function Results post-Screening		ETP, SAC
42.	mITT	S3	Listing of Asthma Exacerbations	Include a column for severity	ETP, SAC
43.	mITT		Listing of Asthma Control Questionnaire (ACQ-5)		ETP, SAC
44.	mITT		Listing of St George's Respiratory Questionnaire (SGRQ)		ETP, SAC
45.	mITT		Listing of Peak Exploratory Flow (PEF)		ETP, SAC
46.	mITT		Listing of Fractional Exhaled Nitric Oxide (FeNO)		ETP, SAC
47.	mITT		Listing of Daytime and Night-time Asthma Symptoms		ETP, SAC
48.	mITT		Listing of Rescue Medication Use		ETP, SAC
49.	mITT		Listing of Hospitalisations and Emergency Room Visits		ETP, SAC
50.	PK		Listing of Serum GSK3772847 Concentration		SAC Only

**CONFIDENTIAL**

207597

Non-ICH: Listings					
No.	Population	IDSL / Example Shell	Title	Programming Notes	Deliverable [Priority]
51.	mITT		List of Free and Total Soluble ST2 Concentrations		
Adverse Events					
52.	SAFF_ALL		Listing of Clinical Chemistry		ETP, SAC
53.	SAFF_ALL		Listing of Haematology and Cardiac Markers		ETP, SAC
54.	SAFF_ALL		Listing of Anti-GSK3772847 Antibodies		ETP, SAC
55.	SAFF_ALL	ESI8	Listing of AE Terms of Special Interest	IDSL	ETP, SAC
Exploratory Biomarker					
56.	mITT		Listing of Induced Sputum and Exploratory Serum Biomarkers		ETP, SAC
Medical History					
57.	SAFF_ALL	MH2	Listing of Medical Conditions at Screening		ETP, SAC
58.	SAFF_ALL	SP5	Listing of Family History of Cardiovascular Disorders		ETP, SAC
59.	SAFF_ALL	SP6	Listing of Asthma History		ETP, SAC
60.	SAFF_ALL	SP7	Listing of Smoking History and Smoking Status		ETP, SAC
61.	SAFF_ALL	CM6	Relationship between ATC Level 1, Ingredient and Verbatim Text		ETP, SAC
Liver Events: Note only produced if there is a Liver Event					
62.	SAFF_ALL	LIVER5	Listing of Liver Events		ETP, SAC
63.	SAFF_ALL	LIVER6	Listing of Liver Event Information for RUCAM Score		ETP, SAC
64.	SAFF_ALL	LIVER7	Listing of Liver Biopsy		ETP, SAC

Non-ICH: Listings					
No.	Population	IDSL / Example Shell	Title	Programming Notes	Deliverable [Priority]
65.	SAFF_ALL	LIVER8	Listing of Liver Imaging Details		ETP, SAC
Cardiovascular Events: Note only produced if there is a Cardiovascular Event					
66.	SAFF_ALL	Patient Profile	Listing of Myocardial infarction/unstable angina		ETP, SAC
67.	SAFF_ALL	Patient Profile	Listing of Congestive heart failure		ETP, SAC
68.	SAFF_ALL	Patient Profile	Listing of Arrhythmias		ETP, SAC
69.	SAFF_ALL	Patient Profile	Listing of Valvulopathy		ETP, SAC
70.	SAFF_ALL	Patient Profile	Listing of Pulmonary hypertension		ETP, SAC
71.	SAFF_ALL	Patient Profile	Listing of Cerebrovascular events/stroke and transient ischemic attack		
72.	SAFF_ALL	Patient Profile	Listing of Peripheral arterial thromboembolism		
73.	SAFF_ALL	Patient Profile	Listing of Deep venous thrombosis/pulmonary embolism		
74.	SAFF_ALL	Patient Profile	Listing of Revascularisation		
75.	SAFF_ALL	Patient Profile	Listing of Deaths		

